## Statistical Analysis

### Formative evaluation

During and after the study, we will conduct a qualitative assessment to evaluate the implementation of the proposed diabetes self-management program. Qualitative information to be analyzed will include coaches notes, descriptions of requests for technical support, observations of home visits, and information provided through participant surveys. The purpose of this study is to generate insights that will inform a future, larger study evaluating the effectiveness of the program across a larger study population. While we will measure many of the same outcomes in that future study, the design and implementation will evolve based on the results of the current study. We intend to conduct multivariate analyses to evaluate program implementation performance in various subgroups; for example, we will evaluate enrollment rates, program completion rates, and other participation metrics against participant demographics and disease progression measures. This analysis will be carried out using intent-to-treat analysis principles.

### Program effectiveness

While it is not the primary aim of this study, the data we collect will be used to evaluate the program's effectiveness in maintaining participants' glycemic control. We will evaluate changes in participants' A1C measurements over time, as well as summary statistics of interstitial glucose measurements obtained from CGM devices, similar to those examined by Lind et al. (Lind, 2017). Endpoints of interest to this analysis include but are not limited to average measured glucose levels over the course of the study, glucose variability, and frequency and nature of medical care utilization throughout the study timeframe. This analysis will provide insight into patients' ability to self-manage their glucose levels using the program, as well as help refine the program and inform the design of a future, larger study of its effectiveness.

All eligible participants will be included in the analysis.

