## Consent

Because the claims data used to assess patient eligibility will lag by two months (and thus may not capture very recent events or diagnoses) patients will be asked in the consent form to review the eligibility criteria and confirm that they meet it before signing the form.

To assure informed consent, prospective patients who receive study materials in the mail will be given at least two days to review the consent form and the opportunity to talk with a program representative who has been trained in human subjects research. Patients who attend an educational class, receive a home visit, or come to the clinic to learn about the study will be given ample time to read the consent form, the opportunity to take the consent form home (if applicable), and as much time as needed to talk with a program representative about the study. Patients with any medical concerns that they feel may affect their participation will be referred to their providers.

Patients will also be provided with a manufacturer resource phone number should they have any technical support questions related to the CGM system. Patients can call their coach or request in-person assistance on how to apply and setup the CGM system. The consent form itself will contain safety information related to study devices. Patients will also receive web links to the CGM system and activity tracker terms and conditions and privacy policies that they may view prior to providing consent. We will ask patients to review and agree to these terms prior to receiving their devices so that patient accounts can be created for the smartphone apps, thus reducing the set-up burden for the participant. Once participants receive their devices, this link will also be accessible on the smartphones for reference.

Patients will be able to provide consent either by signing a paper copy and returning it in the mail or in person (e.g. at a class, during a home visit, or at an in-clinic meeting). Patients will not receive devices prior to completing the informed consent.

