## 7. Selection and Withdrawal of Subjects

Study participants will be recruited from UnitedHealthcare members in the Las Vegas area who are enrolled in a Medicare Advantage plan (Senior Dimensions®). To be eligible for the program, patients must meet specific inclusion/exclusion criteria. All Medicare Advantage patients who meet this criteria will be invited to participate in the program regardless of their latest A1C test.

We intend to enroll 500 program participants (defined as those to whom program materials and devices have been delivered). When 500 participants have been enrolled, any patients that have been recruited but who have not yet been enrolled (including those who may have signed a consent form) will be asked if they would like to be notified of any other upcoming study opportunities for which they may be eligible.

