## Exclusion Criteria

Patients will not be eligible if any of the following criteria pertain to them:

- Pregnant
- Blind
- Deaf
- Receiving chemotherapy or radiation therapy to treat cancer (either now or within the last six months)
- Misusing any drugs (including alcohol, painkillers, hallucinogens, or others)
- Critically ill
- Diagnosed with or experiencing:
  - Kidney disease stages 4 and 5
  - End stage renal disease
  - Severe liver disease
  - Dementia
  - Schizophrenia
  - Bipolar disorder
  - Autism
  - An intellectual or learning disability
  - Arrhythmias other than atrial fibrillation
  - Congestive heart failure
- Has had a:
  - Myocardial infarction within the last 6 months
  - Stroke within the last 6 months
  - Stroke that resulted in significant disability (e.g., unable to write clearly or walk)

When a patient is referred to the program by the clinic and this patient is not eligible due to a diagnosis of congestive heart failure, one of the study's medical advisors will make a clinical judgement as to whether the severity of the patient's congestive heart failure warrants exclusion from the study.

Initial eligibility will be determined using medical and pharmacy claims data. Since these claims will not address all inclusion and exclusion conditions, patients will confirm their eligibility by reviewing the eligibility criteria provided in the consent packet and the consent form, and attesting to their eligibility by signing the consent form.

If during the study a patient's status changes such that s/he is no longer eligible to participate, the patient will be removed from the study and will be asked to return all devices (with the exception of used sensors, the used transmitter, and the glucometer if the patient received one).

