### Data Collection

Since our program achieves its efficacy through education, self-discovery, and the behavior change that results from that education, we will collect data about our ability to connect with and engage participants in the program. Specifically, we will collect data on recruitment efforts (e.g., recruitment rate; patient preferences in setting up their devices (i.e., via self-start, home visit, or in-class); information related to study enrollment (e.g., method and date of enrollment, pre-program survey); and program engagement metrics (e.g., device calibrations, use of companion mobile application, CGM component completion rates). By enrolling in the study, participants consent to the acquisition, review, and analysis of data from their medical records. We will also collect the following data, which will allow us to both evaluate the program as delivered, and to help us tailor future versions of the program to better serve the participants that we enroll:

- Reasons for declining to participate, as given to program personnel at different contact points
- Recordings of coaching calls and introductory training sessions
- Observations from coaches about the most effective calling procedures, behavioral strategies, talking points, and online facilitation techniques
- Time dedicated to device preparation, and to each aspect of the introductory training session
- Total letters sent, and the number returned due to bad addresses
- Recruitment strategies to which each potential participant was exposed
- Total coaching calls attempted and completed per participant, and the durations of those calls
- Suggestions made during coaching calls and during the exit interview about how to improve the program
- Demographic information such as age, education, and social support
- Survey results to assess familiarity with technology such as computers and smartphones, knowledge about nutrition and self-care, and self-efficacy in disease management.

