A secondary goal is to evaluate the effectiveness of the program as implemented in this study. On all patients we will collect interstitial glucose levels from the CGM device, activity and other available data from the activity tracking device, any changes in prescription medication use during the normal course of participants' medical care outside of the study, routine lab measures, any changes in mental health (specifically depression), and total costs of medical care before, during, and after the study. Patients will be asked to share information contained in their medical records and claims through December 31, 2027, even if patients stop early from participating in the study.

The following measurements will be collected from study participants:

Data Elements from Participants	Source	Data Collection Time			
		Study Enrollment	During course of study	CGM Completion (10 weeks)	Post-Program through 12/31/27
Age	Medical Record 	X			
Time since diabetes diagnosis	Enrollment Survey 	X			
Race/Ethnicity	Enrollment Survey 	X			
Hemoglobin A1C	Medical Record	X		X	X
Diabetes Distress Questionnaire	Enrollment Survey 	X			
Cancer Indicator	Medical Record 	X			
Heart Failure Indicator	Medical Record 	X			
Diabetes medication indicator	Medical Record 	X		X	X
Metformin indicator	Medical Record 	X		X	X
Glipizide indicator	Medical Record 	X		X	X
Pioglitazone indicator	Medical Record 	X		X	X
Rosiglitazone indicator	Medical Record 	X		X	X
Sitagliptin indicator	Medical Record 	X		X	X
Linagliptin indicator	Medical Record 	X		X	X
Saxagliptin indicator	Medical Record 	X		X	X
Exenatide indicator	Medical Record 	X		X	X
Liraglutide indicator	Medical Record 	X		X	X
Glyburide indicator	Medical Record 	X		X	X
Basal insulin indicator	Medical Record 	X		X	X
Bolus insulin indicator	Medical Record 	X		X	X
Other prescription drug use	Medical Record 	X		X	X
Interstitial glucose levels	CGM device 		X	X	

Contacts with program coaches	Coaching platform 		X	X	X
Interactions with secure texting	Digital app 		X		X

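### Does limiting the effectiveness analysis to eligible participants leave it open whether heart-failure patients admitted on a medical advisor's judgement are analysed?

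*Combined protocol and SAP*

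**What the plan says.** The effectiveness set is given in Section 10, Program effectiveness: "All eligible participants will be included in the analysis". The word eligible is not defined there.

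Section 7 ties eligibility to the inclusion and exclusion criteria, and the Exclusion Criteria list names congestive heart failure without a severity limit. A paragraph after the list deals with clinic referrals. When "this patient is not eligible due to a diagnosis of congestive heart failure", a medical advisor judges whether the severity of the "congestive heart failure warrants exclusion from the study". The section then explains that claims cannot cover every criterion, so patients complete the check by "attesting to their eligibility by signing the consent form". Section 6 (Consent) gives a related reason for the attestation: the claims data "will lag by two months (and thus may not capture very recent events or diagnoses".

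Participation is defined separately. Section 7 plans for 500 "program participants (defined as those to whom program materials and devices have been delivered", so the term rests on delivery.

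In Section 10, Data Collection, record access follows enrollment: "By enrolling in the study, participants consent to the acquisition, review, and analysis of data from their medical records". It continues even if the patient stops early. The data table there includes a "Heart Failure Indicator" at enrollment. The intent-to-treat statement appears under Formative evaluation, not under Program effectiveness.

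**The concern.** Read literally, the plan seems able to create people who are participants but not eligible participants. A clinic-referred patient with heart failure has a listed exclusion, is cleared by the advisor, receives the devices and is enrolled. If eligible means accepted into the study, that person is analysed. If it means free of every listed exclusion, that person is dropped. The attestation does not obviously settle the matter, because the list being attested to includes heart failure. The indicator collected at enrollment would make the narrow reading easy to apply, even after results are known.

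A second group could raise the same question: participants whose later records show that they already met an exclusion when they signed, because the screening claims were out of date.

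At stake is whether the effectiveness set can be reproduced. Medical care utilization is one of the named endpoints. If people with heart failure use more care than the rest, leaving them out would make utilization look lower, in results meant to inform a larger study.

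**Working it through.** **Which reading the text supports**

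1. *When the label applies.* In the Exclusion Criteria section, the statement that "this patient is not eligible due to a diagnosis of congestive heart failure" describes the patient at referral. The advisor's decision comes afterwards. No sentence calls a patient ineligible once the advisor has found that exclusion is not warranted.
2. *Status of the advisor's step.* It stands in the Exclusion Criteria section and qualifies one item on that list. A patient who passes it has been selected by Section 7's own procedure.
3. *Direction of the analysis sentence.* It says who is included. It sets out no step for removing enrolled people and no re-check of baseline eligibility.
4. *Role of the indicator.* The "Heart Failure Indicator" is listed with other enrollment variables such as age and a cancer indicator. Nothing links it to the definition of the analysis set.
5. *Late-emerging diagnoses.* The plan recognises the claims lag and answers it with the attestation. No section provides for judging baseline eligibility again from later records.
6. *Removal during the study.* Section 7 removes a patient whose status changes from participation and asks for the devices back. It does not discard that patient's data.

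**Size if the narrow reading were used anyway**

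The only input from the documents is the enrollment target of 500, and no sample size calculation lies behind it. The other inputs are assumptions: p, the share left out; m, their utilization relative to the others; and d, the difference in A1C change.

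Set the others' mean utilization to 1. The full mean is then 1 + p(m − 1), and the relative understatement from leaving the group out is

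p(m − 1) / [1 + p(m − 1)].

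The shift in mean A1C change is p × d.

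| Left out of 500 | p | Understatement, m = 2 | Understatement, m = 3 | A1C shift, d = 0.5 points |
|---|---|---|---|---|
| 1 | 0.002 | 0.002/1.002 = 0.20% | 0.004/1.004 = 0.40% | 0.001 |
| 5 | 0.01 | 0.01/1.01 = 0.99% | 0.02/1.02 = 1.96% | 0.005 |
| 25 | 0.05 | 0.05/1.05 = 4.76% | 0.10/1.10 = 9.09% | 0.025 |

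Tipping point for a 5% understatement: p(m − 1) = 0.05/0.95 = 0.0526. With m = 2 this needs 0.0526 × 500 = 26.3 participants. With m = 3 it needs 26.3/2 = 13.2.

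If everyone admitted is analysed, p = 0 and every entry is zero.

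**The case for a change.** The case for a change is that the natural reading is not written down. Section 7 equates eligibility with meeting the criteria, and it speaks of an enrolled patient who later stops being eligible, so the protocol does not treat eligible and enrolled as the same thing. The consent attestation makes no exception for a patient admitted on the advisor's judgement. The intent-to-treat sentence belongs to a different analysis. One sentence would close the gap, need no new data, and remove any freedom to choose the set after seeing results.

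Much of this stands as a remark on drafting. No sentence expressly places these patients in the effectiveness set, and the attestation wording fits loosely with the advisor route. What does not stand is the step from loose wording to a real fork in the analysis. The narrow reading would have an advisor clear a patient individually, the program supply devices and coaching for 10 weeks, and an analyst then drop that patient for the very condition that had been cleared. Nothing in the plan calls for that. The freedom to choose afterwards also has little to act on: a descriptive, open-ended list of endpoints, with no comparison group and no test.

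The late-diagnosis group adds little. The attestation is the plan's stated answer to the claims lag, and what remains is a possibility in any study that screens on claims.

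**Conclusion.** No change is needed. This is a missing definition that analysts would fill in the obvious way, by including everyone admitted to the program, and on that reading nothing changes numerically. On the narrow reading, leaving out 1 to 5 of 500 would lower mean utilization by 0.2% to 2.0% if those patients used two to three times as much care as the others. Mean A1C change would move by 0.001 to 0.005 points if they differed by 0.5 points. These counts, ratios and differences are assumptions, because the documents supply none of them. A 5% shift in utilization would need about 13 to 26 people to enter by a route open only to clinic-referred heart-failure patients whom an advisor has cleared.

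The plan describes itself as exploratory, sets no hypothesis test and does not make effectiveness its primary aim. A formal definition would tidy the wording but would not change what the study can conclude. The "Heart Failure Indicator" already lets analysts count participants with heart failure and describe them if they wish. Nothing here bears on which patients should be admitted.

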## 11. Direct Access to Source Data/Documents

The Sponsor-Investigator, Dexcom, and the study doctor will permit any program-related monitoring, audits, IRB/IEC review, and regulatory inspection(s), deemed necessary by the IRB, and will provide direct access to relevant source data/documents as may be required.

## 12. Risks

This is a minimal risk study. Program participants are being asked to wear a Fitbit activity tracker and a Dexcom CGM system.

### Risks of the Activity Tracker Device

The Fitbit has a wrist band. Skin irritation from these devices is a remote possibility (there are very few reports in the online literature regarding this occurrence with similar devices). Study participants who experience skin irritation will be instructed to remove the activity tracker during sleep, and/or to alternate wearing it on the opposite wrist. There is also a slight risk that the privacy of the activity tracker data could be exposed if an unauthorized source hacks into the activity tracker's data system. Due to security and authorization that Savvysherpa has in place this risk is minimal.

### Risks of CGM

When the wire-like sensor is deployed by the applicator, participants can expect a sensation similar to a needle insertion for a blood draw. Risks of CGM use include discomfort during sensor insertion, along with pain, inflammation, redness, swelling, minor bleeding and minor infection at the sensor insertion site. Participants might also experience these symptoms as a result of contact between the adhesive pad of the sensor and the skin. In rare cases, an infection can spread to other parts of the body.

Allergic reactions can develop in response to the sensor, the adhesive, and other parts of the CGM. If these symptoms occur, participants have the ability to remove the CGM at will and can anticipate that their symptoms will clear up within one week.

The sensor and/or applicator may fracture during use. If a sensor remains in the skin, there is minimal risk to the patient as long as a physician confirms there are no symptoms of infection or inflammation.

Patients will be advised that the investigational sensor, transmitter, and smartphone must be removed before Magnetic Resonance Imaging (MRI), Computed Tomography (CT) scan, or diathermy treatment. The device is MR Unsafe. Participants should not bring any portion of the device into the MRI environment. The Dexcom IUO CGM System has not been tested during MRI or CT scans or with diathermy treatment. The magnetic fields and heat could damage the device, causing it to stop displaying glucose readings, display inaccurate glucose readings, or prevent alerts.

Patients will also be advised of CGM system warnings that may affect the proper operation of the device and/or the patient's safety. These warnings will be described in the informed consent and authorization form, and in the informational materials provided to patients when they receive their systems.

Patients will be provided with a phone number for Dexcom's Technical Support. Staff for this line will be well-qualified to address any potential questions and risks associated with the investigational device. Significant or serious health risks with CGM are not anticipated.

The same precautions have been taken to code and/or encrypt the investigational system's electronic data as have been taken with the commercial Dexcom devices. Regardless, throughout the program, patients will be advised not to rely on the device to make any treatment decisions, and to measure their blood glucose in order to confirm any symptoms of hypoglycemia.

#### Risks of Glucose Meter

Finger-stick blood samples will be taken during this study. This may cause some discomfort, pain, bruising, and/or soreness afterwards. Rarely, an infection may occur. Routine finger-stick sampling for use with a blood glucose meter is already standard-of-care for T2D patients.

#### Risks of Medical Record Review and Data Collection

This project involves extracting Protected Health Information (PHI) from patients' medical records. PHI will also be extracted from Dexcom patient databases. Activity tracker data will be synced via https from the trackers to the secure servers of Fitbit. Data collected from the activity trackers will then be sent via https to Savvysherpa's secure servers. Personally Identifiable Information (PII) will be collected from health providers, Dexcom, and/or Fitbit, as well as through survey responses, coach-patient texts, call recordings, online program engagement, and/or in-person group participation at educational classes. The combined dataset will be de-identified by removing personal identifiers from each system and replacing them with a unique study identifier.

The combined data set will be stored in Savvysherpa's HITRUST-certified secure server environment that can only be accessed by authorized personnel via a physically secured room. Any links between personal identifiers from the source systems and study identifier will be deleted ten years after study completion. Recordings of educational classes, coaching sessions, and coach-patient texts will also be deleted ten years after study completion. PII associated with these recordings may be visible to program staff and Dexcom in the course of quality improvement efforts and the development of training, but the identities and privacy of participants will otherwise be maintained.

There is a risk that the information could be inadvertently disclosed to another entity although the risk is very small given the data security measures in place.

